2.2 Secondary Objectives

To determine if albuterol is as effective as 7% HS in accelerating MCC. We will also evaluate the safety of HS in moderate to severe asthmatics by determining the proportion who are 'intolerant' to HS treatment (see Section 5.3).

3. INVESTIGATIONAL PLAN (brief overview)

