temperature, respiratory rate (RR), heart rate (HR), oxygen saturation, blood pressure (BP), and symptom questionnaires will be collected. Fractional exhaled Nitric Oxide (FeNO) will be measured in exhaled breath (used to classify asthma as being predominated by eosinophilic vs non-eosinophilic airway inflammation). Spirometry will be performed to establish that day's baseline values. FEV1 must be $\geq 70\%$ before albuterol. Participants will inhale Tc99m-SC and immediately be scanned by gamma scintigraphy to measure deposition of the radiolabeled particles in the airways (4 minute scan). MCC will be assessed over a 2-hour period to define baseline MCC. A baseline symptom questionnaire will be obtained. Subjects will then undergo a sputum induction procedure

Any subject who experiences a $\geq 10\%$ reduction in FEV1 from that day's baseline at the spirometry measure, or who increases HR, BP or RR more than 30% from baseline, or with audible wheezing on physical exam, or participants who report any symptom as severe (score of 3) on the symptom questionnaire will be considered intolerant to HS and will not be included in further study. Oxygen saturation will be monitored, and a transient decrease is an expected finding when using mucolytic agents. Sustained ($< 90\%$ for more than 1 hour) decrease in oxygen saturation will be considered intolerance. Testing will be stopped at any point the volunteer requests that it stop. Any subject who does not tolerate HS will be monitored until the vital signs return to normal limits, and the symptoms resolve. Subjects will be discharged to home with contact information for a study physician, an asthma action plan reviewed by the study coordinator, and emergency medications if needed overnight, including an albuterol MDI with spacer and 60 mg of prednisone. Subjects will be instructed to call the physician on call if they require prednisone treatment.

4.2 Visit 2 Follow-up Baseline Visit: Participants will return the following morning for vital signs, symptom questionnaire, 24-hour lung retention imaging, FeNO, and spirometry. Subjects who tolerate the HS dose and do not meet stopping criteria will be invited back for the remaining study visits.

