4.5 Visit 5 Treatment (effect of 7% HS on MCC): Subjects will return at least 1 week, but no more than 6 weeks later to the lab. This visit may be delayed longer if the subject has an asthma related exacerbation to ensure good health for a total of 4 weeks before the visit. Vital signs, symptom and radiation exposure questionnaire are collected, and FeNO and spirometry performed. A negative urine pregnancy test will be required of all female participants. Medical history will be updated, including any new medication. FEV1 must be at least 10% of baseline (established at screening visit) and $\geq 70\%$ of predicted for age, height, sex, and race/ethnicity. Subjects will undergo spirometry and FEV1 must be at least $> 70\%$ of predicted for age, height, sex, and race/ethnicity. Participants will then inhale Tc99m-SC and immediately be scanned by gamma scintigraphy to measure deposition of the radiolabeled particles in the airways (4 minute scan). While they remain seated in front of the gamma camera, they will be provided with 4 puffs of albuterol with spacer, followed by a 15-minute wait period. They will then inhale 4 mL of nebulized 7% HS. MCC measurement will be performed for a 2-hour period post-radioaerosol inhalation (which includes the period of HS inhalation) to measure acute effects of HS on MCC. Vital signs and symptom questionnaire will be performed at 5 and 30 minutes after HS inhalation while sitting in front of the gamma camera. Vital signs, symptom questionnaire, spirometry and discharge procedures will be identical to those described for visit 1.

Subjects will undergo sputum induction following the MCC scan.

4.6 Visit 6 Follow-up HS treatment Visit: Participants will return the following morning for vital signs, symptom questionnaire, 24-hour lung retention imaging, FeNO, and spirometry.

4.7 Visit 7 Study Discontinuation: The subject will return to the research lab 5-10 days after the completion of the treatment visits for AE inquiry, vital signs and spirometry.

4.8 Unscheduled visits: Any subject who has an unexpected problem as a result of the study treatment will have access to a study physician. Subjects will be invited back to the lab for vital signs collection, physical exam, and spirometry. If the subject has any adverse event not associated with the study, he/she will not complete the study until the AE resolves such that it does not interfere with the study or with safety.

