For the baseline MCC measurement, the gamma image capture will begin immediately and will capture continuously for the first 34 minutes. Thereafter, 2 consecutive 2-minute images will be obtained at the start of every 10-minute period until 2 hours have passed. For visit 3/5, participants will first inhale Tc99m-SC as described above then sit in front of the gamma camera for 4 minutes during which images of the lung will be continuously captured. While still sitting in front of the gamma camera, they will inhale HS. Image capture will be continuous during HS inhalation and for the next 34 minutes, after which 2 consecutive 2-minute images will be obtained at the start of every 10-minute period until 2 hours have passed. The subject will also return the day (visit 4/6) following each MCC measurement to sit in front of the gamma camera for 30 minutes to obtain images of the lungs to visualize retention of Tc99m-SC particles. No Tc99m-SC will be administered at this visit. Spirometry, symptom questionnaire, and vital signs will be collected prior to discharge on the follow up day.

Hypertonic Saline Induced Sputum procedure:

Prior to sputum induction, subjects will have spirometry measured for FEV1 and FVC values. Next, an ultrasonic nebulizer filled with 20 cc of 3% hypertonic saline (inhalation grade for respiratory use only, 3% NaCl) will be set to the maximum output setting and turned on. The subject will be instructed to latch his/her mouth onto the nebulizer mouthpiece and breathe normally (i.e., tidal breaths) for 7 minutes as the saline is nebulized through the mouthpiece in a jet stream and inhaled. The nose will not be occluded for this procedure. The subject will be encouraged to come off the mouthpiece at any time to cough if a sputum sample from the lower

[figure not shown]

Figure 2. (A) Initial deposition of radiolabeled particles (top) and 20 minutes later (bottom) in the lungs of an asthmatic subject detected with gamma scintigraphy.

(B) MCC expressed as retention of labeled particles vs time. In our prior study of gamma tocopherol (Vitamin E) vs placebo, LPS challenge reduced MCC during placebo (squares) but not during active treatment (diamonds).

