airways (i.e. not from the back of the throat) is ready for expectoration. Prior to expectoration, subjects will be asked to blow their nose, rinse their mouth with water, and clear their throat to avoid the inclusion of non airway fluid samples. The sample will be expectorated into a sterile specimen jar and capped.

Following the measurement of FEV1 after the first 7 minute inhalation period, the concentration of saline will be increased from 3% to 4%, provided the FEV1 decrement is < 10% from the post bronchodilator value. If the FEV1 falls between 10-20% of the post bronchodilator value, the test will proceed but the concentration of saline will remain the same. If the FEV1 falls by > 20% or if troublesome symptoms occur, the nebulization will be discontinued, and albuterol will be immediately available if necessary to relieve symptoms. The same procedure will be followed for the final 7 minute inhalation period using 5% hypertonic saline provided the FEV1 safety parameters described above have been met. The nebulization is stopped after a total of 21 minutes or earlier if a sputum sample of good quality is obtained (i.e. visible sputum plugs). Subjects may request early termination at any time the procedure becomes intolerable.

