6.2 Secondary Endpoints

a. change in MCC from baseline immediately after albuterol inhalation. This endpoint is of exploratory interest.

b. Safety measures for HS treatment in moderate to severe asthmatics will include change in the following from baseline:

- Vital signs (HR, RR, BP and oxygen saturation)
- Spirometry (FEV1, FVC)
- Symptom Questionnaires
- Physical exam (wheezing on chest auscultation, for example)

We will also assess:

- Adverse events and Serious Adverse events
- Proportion of participants who are deemed 'intolerant' to HS (i.e. those who experience a persistent reduction in FEV1 of $\geq 10\%$ from that day's baseline at 30 minutes post-HS, those who report shortness of breath, those who report a score of "3" for any individual symptom criterion, or those who experience oxygen saturation levels below 90% for > 1 hour).

Safety endpoints will be assessed continuously during the study period for monitoring of adverse events and individual stopping criteria. All adverse events whether or not listed in the NCI-CTCAE (see Section 9) or whether they are or are not related to study participation will be graded on a scale from 1 to 5 according to the standards in the NCI-CTCAE manual. Adverse events will be reported to the UNC IRB, the UNC DSMB, and the NHLBI project officer. The DSMB will review the protocol after 5 subjects have completed study procedures or at 6 months after enrollment begins, whichever is soonest, and then every 6 months thereafter.

Exploratory endpoints will also be assessed. These will focus on sputum cellularity, mediators in sputum (e.g. T1 cytokines: IL-1 β , IL-6, IL-8, TNF α , T2 cytokines, IL-4, IL-5, IL-13), eicosanoids,

and mucins (total mucins, MUC5AC, MUC5B).

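### Visit 1 reactors are removed before 7% HS is first given, so neither intolerance proportion in the plan gives 7% HS intolerance in the population named in Section 2.2

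*Combined protocol and SAP*

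**What the plan says.** Section 2.2 sets a safety objective: to "evaluate the safety of HS in moderate to severe asthmatics by determining the proportion who are" intolerant. Section 6.2 lists the endpoint as "Proportion of participants who are deemed" intolerant to HS. It defines this by events after HS, including an FEV1 fall of at least 10% that persists 30 minutes post-HS, but names no visit and no denominator. Section 6.3 and the synopsis commit to a proportion, with a 95% confidence interval, of enrolled patients who do not tolerate HS at baseline.

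The schedule runs as follows.

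- **Visit 1 (Section 4.1).** After the baseline scan, "Subjects will then undergo a sputum induction procedure". Section 5 describes the induction as starting with "an ultrasonic nebulizer filled with 20 cc of 3% hypertonic saline", stepping to 4%, and then: "The same procedure will be followed for the final 7 minute inhalation period using 5% hypertonic saline". Section 4.1 goes on to say that a subject who meets its reaction criteria "will be considered intolerant to HS and will not be included in further study".
- **Visit 2 (Section 4.2).** "Subjects who tolerate the HS dose and do not meet stopping criteria will be invited back for the remaining study visits".
- **Visit 5 (Section 4.5).** "They will then inhale 4 mL of nebulized 7% HS". The procedures table has a single mark for nebulized HS, in the Visit 5 column.
- **Section 4.11** adds criteria that must be met before HS is inhaled.

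**The concern.** Subjects are screened on their reaction at a visit with weaker saline before they can receive the test article. Two different proportions can be read from the plan, and neither answers Section 2.2. The Section 6.3 figure keeps the Visit 1 reactors but is tied to a visit at which no 7% HS is scheduled. A figure built from the Section 6.2 criteria after 7% HS can come only from subjects who passed the Visit 1 screen and the Section 4.11 criteria. If sensitivity to induction saline and to 7% HS go together, those most likely to react to 7% HS have left before it is given.

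At stake is the headline safety statement of an open-label study of 28 subjects. At that size a handful of removals can change the apparent rate twofold, and nothing in the plan says the result is conditional.

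**Working it through.** The plan gives no expected intolerance rate and no precision target for it, so there is no figure of its own to reproduce. The numbers 21 and 28 in Section 6.4 are for the MCC comparison and serve here only as group sizes. All rates below are assumptions.

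**Model.** Let *p* be the true 7% HS intolerance among enrolled subjects, *s* the chance of Visit 1 removal for those who would not tolerate 7% HS, and *f* the same chance for those who would.

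- Share removed at Visit 1: r = ps + (1−p)f
- Visit 5 rate among those remaining: v = p(1−s)/(1−r)
- Intolerant at either visit, over enrolled: c = r + p(1−s) = p + (1−p)f

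**Direction.** v < p requires 1−s < 1−ps−(1−p)f, which reduces to s > f. If s = f there is no bias; if s < f, v overstates.

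**Numbers for p = 20%, f = 5%:**

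| s | r (removed/enrolled) | v (Visit 5 rate) | c (either visit) |
|---|---|---|---|
| 0% | 0 + 0.04 = 4% | 0.20/0.96 = 20.8% | 24% |
| 25% | 0.05 + 0.04 = 9% | 0.15/0.91 = 16.5% | 24% |
| 50% | 0.10 + 0.04 = 14% | 0.10/0.86 = 11.6% | 24% |
| 75% | 0.15 + 0.04 = 19% | 0.05/0.81 = 6.2% | 24% |

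Keeping f = 5% and s from 25% to 75%, v runs from 8.1% to 2.8% when p = 10%, and from 25.3% to 10.1% when p = 30%.

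Two things follow. The Section 6.3 type of figure (column r) is not an estimate of p: it moves from 9% to 19% with *s* while p stays at 20%. The composite c exceeds p by (1−p)f = 4 points whatever *s* is, because it adds subjects removed early who would have tolerated 7% HS. The gap between c and v is therefore not the size of the bias.

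**Precision, with illustrative counts.** Suppose 28 are enrolled, 4 are removed as intolerant before Visit 5, 3 are lost for other reasons, and 2 of the remaining 21 are intolerant at Visit 5. The exact (Clopper-Pearson) 95% intervals are:

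- Visit 5, among those dosed: 2/21 = 9.5% (1.2 to 30.4)
- Removed earlier: 4/28 = 14.3% (4.0 to 32.7)
- Composite: 6/28 = 21.4% (8.3 to 41.0)

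**Criteria side by side.** Section 4.1 counts audible wheeze and a rise of more than 30% in heart rate, blood pressure or respiratory rate; the Section 6.2 definition has none of these. Section 6.2 counts any shortness of breath and requires the FEV1 fall to persist at 30 minutes; Section 4.1 does not. The induction procedure continues, at an unchanged concentration, when FEV1 falls by 10-20%, whereas Section 4.1 removes a subject at 10%.

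**The case against.** A reader might infer that the plan defines a Visit 5 intolerance proportion and that it understates intolerance. The documents support neither step as a flat statement. No section names such a proportion. The sentence in Section 6.3 and the synopsis uses enrolled patients, and on its wording counts the Visit 1 reactors. Section 6.2 would also allow them in, since Section 4.1 deems them intolerant. This stands, but it does not rescue the endpoint: so read, the figure describes reactions at a visit without scheduled 7% HS.

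The downward direction needs s > f. That is plausible, since both exposures are hypertonic saline and Section 4.1 itself labels reactors intolerant to HS. It is not shown, and the triggers include non-specific ones such as a heart-rate rise or a severe headache.

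Three further limits also stand.

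- Removal after the Visit 3 induction is only inferred. Section 4.4 refers to stopping criteria, while the individual criteria in Section 4.11 apply after HS inhalation.
- The earlier exposure varies, because induction stops once a good sample is obtained. Section 3.1 also places Visit 1 spirometry before induction, so it is unclear whether the FEV1 criterion follows any saline.
- Removals are not hidden. Section 9 makes failure of a safety criterion an adverse event, and Section 6.2 includes adverse events. They are simply not tied to the intolerance proportion.

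Finally, Sections 4.2 and 5.3 read as if HS is given at Visit 1. Sections 3.1 and 4.1 and the procedures table schedule no nebulized 7% HS there, and the point rests on that schedule.

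**Conclusion.** The concern holds in a conditional form. On the visit schedule, subjects labelled intolerant at Visit 1 leave before 7% HS is first given. The committed baseline proportion does not measure 7% HS intolerance. A post-HS proportion at Visit 5 is conditional on passing the Visit 1 screen and the Section 4.11 criteria. Neither supports a conclusion for moderate to severe asthmatics in general.

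A Visit 5 figure is likely to be too low if Visit 1 reactors are also likelier to react to 7% HS. In the assumed case of 20% true intolerance it would read between 16.5% and 6.2%. That range depends entirely on the assumed *p*, *s* and *f*, and the model leaves out both the Section 4.11 filter and any removal at Visit 3. With about 21 to 28 subjects every interval is wide, so the argument is about what each proportion means, not about a demonstrable difference between them.

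**What to change.** Leave the removal rule unchanged and amend Sections 6.2 and 6.3, naming visit, exposure, criteria and denominator. Report, each with an exact 95% confidence interval:

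- **(a)** intolerance at Visit 5 among subjects given 7% HS, labelled as conditional on tolerating the earlier saline inductions and meeting the pre-HS criteria;
- **(b)** the number and proportion removed as intolerant at earlier visits, over all subjects who had a first saline exposure;
- **(c)** the combined proportion over that same group, stated to be a composite of 3-5% induction and 7% HS that includes non-specific triggers and counts subjects lost for other reasons as non-events, and so is not a strict upper bound.

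Word the Section 2.2 safety conclusion for group (a), with (b) and (c) beside it. The sponsor must also reconcile the passages that disagree on whether HS is given at Visit 1 (Sections 4.1, 4.2 and 5.3 and the procedures table) and on the intolerance criteria (Section 4.1, Section 6.2 and the induction procedure).

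The cost is SAP wording and a few table rows from data already collected. The price is a less favourable headline and three figures to explain instead of one.

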Criteria for Inclusion and Exclusion:	
 1. Age 18-60. 2. Moderate to severe asthma at baseline (determined by Step 3 therapy or greater or by degree of impairment secondary to asthma). Subjects will be Well Controlled asthma at the time of enrollment, or Not Well Controlled as determined by National Heart, Lung and Blood Institute (NHLBI) Expert Panel Report 3 guidelines for diagnosis and treatment of asthma. Subjects who meet the Not Well Controlled criteria must be free of wheezing, and must be at their baseline prior to any hypertonic saline inhalation. 3. Subjects of childbearing potential must be non-pregnant, non-lactating, and using an acceptable method of birth control (an IUD with a failure rate of <1%, hormonal contraceptives, barrier method, or abstinence) for the duration of participation study; if practicing abstinence, the subject must agree to use one of the acceptable methods of contraception if she becomes sexually active.
	Exclusion Criteria
	
 1. Current tobacco smokers (or >10 pack years of smoking) or e-cigarette users (including use within 1 year of the study) 2. Other chronic illness, which could impact safety or study results 3. Radiation exposure within the past year that would cause them to exceed Federal radiation safety regulations.
Study Duration	
Each subject's participation will last up to 4.5 months.
 
The entire study is expected to last up to 6 years.

Study Phases	
Screening	(1) Baseline MCC : Informed consent obtained, medical history including radiation exposure, vital signs and lung function assessed with spirometry. FEV1 must be $\geq 70\%$ of predicted. A baseline MCC scan will be performed over 2 hours.
Study	
Treatment	(2) Baseline MCC with 4 puffs of albuterol : Subjects will return at least 1 week later for a MCC scan with 4 puffs of albuterol immediately after the start of the MCC measurement.
Follow-Up	(3) Acute effects of HS on MCC : At least 1 week after albuterol visit, subjects will receive 4 puffs of albuterol and a dose of 7% HS immediately after the start of MCC measurement over a 2 hour period to assess the acute effects of HS on MCC. Subjects will undergo sputum induction after each MCC visit.

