- **Visit 6 Follow-up HS Treatment Visit:** Participants will return the following morning for a query of symptoms overnight. Spirometry will be performed. Participants will sit in front of the gamma camera for 30 minutes to estimate retention of Tc99m-SC in the airways.
- **Visit 7 Study Discontinuation:** The subject will return to the research lab 5-10 days after the completion of the treatment visits for AE inquiry, vital signs and spirometry.
- **Unscheduled Visits:** There is no expectation for unplanned visits. Subjects will simply be rescheduled if they have a change in health status.

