4.9 Concomitant Medication documentation: Concomitant medications are collected at the screening visit and throughout the study visits. Subjects will use previously prescribed medication for their asthma. Subjects will not be asked to withhold any LABA/steroid combination medication on the morning of study visits. The study will provide all subjects with an albuterol MDI with spacer, and with 60 mg of prednisone as part of the asthma action plan at discharge. Subjects will be allowed to keep albuterol MDI with spacers for their personal use. Subjects will be asked to return unused prednisone tablets to the study staff during the follow-up visits.

4.10 Rescue medication administration: As with any testing in a population of subjects with asthma, albuterol (Ventolin® HFA) will always be available for rescue. There is also a code cart immediately available with epinephrine autoinjectors. Oxygen is available for supplementation if required.

4.11 Subject Completion/ Withdrawal procedures: Subjects are considered completed when the final 24-hour imaging, symptom questionnaire, vital signs and spirometry are collected. Subjects may withdraw at any time. Subjects will be asked to return to the lab for a final visit if they withdraw from the study prior to completion of all study procedures to monitor safety.

Subjects may be withdrawn at any time for safety concerns. Subjects who have any unanticipated problems (UPs) with the study procedures will be monitored until resolution of the symptoms.

Criteria for safety prior to HS inhalation:

(Subjects not meeting these criteria will not proceed with HS inhalation):

1. FEV₁ of at least 70% of predicted
2. FEV₁ within 10% of baseline value established at the screening visit.
2. Baseline oxygen saturation of at least 93%.
3. No history of viral respiratory tract symptoms within 4 weeks of challenge.
4. Vital signs within the previously defined normal parameters.
5. Symptom questionnaire score ≤ 2, , and no more than mild symptoms (ranked as “1”) reported for any category (see Section 5.3).

Criteria for safety of a given individual following HS inhalation which would suspend the individual from further participation in the study will include:

1. A 10% or greater decline in FEV₁ (from that day's baseline) at the 30-minute spirometry assessment.
2. *Continued* Symptoms of asthma exacerbation such as wheezing or respiratory distress.

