HS treatment will be deferred if baseline total symptom score > 2, OR any shortness of breath or fever are reported, OR if any symptom rated as moderate (2) or severe (3). For symptom scores obtained after HS treatment, subjects will be assessed by a study physician if total symptom score >2, if ANY shortness of breath is reported, or if any symptom is rated as moderate (2) or severe (3). If following HS treatment, the participant ranks any symptom as severe (3), that participant will be excluded from further study.

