- **Adverse Event/Serious Adverse Event reporting procedures:** AE's and UP's will be reported to the IRB. The IRB, DSMB, and funding agency will be notified of any SAEs. The DSMB will review progress after the first 5 participants have completed the protocol or at 6 months after enrollment begins, whichever is soonest, and then every 6 months thereafter.
- **Medical Emergency procedures:** There is a study physician available for all inhalation procedures. A code cart and Automated External Defibrillator (AED) are available in the event of a cardiopulmonary event. Albuterol, both inhalers and nebulizers, are available in the event of bronchospasm. If a subject has an event that does not immediately respond to care in the research lab, he/she will be transported via EMS to UNC Healthcare for treatment.
- **Data Safety Monitoring Plan:** Data is initially recorded on paper documents, and the documents are maintained in a binder which is kept in a locked office within the EPA Human Studies facility. The EPA HSF is a secure facility with a guarded entrance and requires identification for entry. This data is then entered into REDCap by an initial data entry person, and confirmed by a second user.

- **Potential Risks:**

Potential Risks of Hypertonic Saline Inhalation:

Inhalation of hypertonic saline carries a small risk of bronchospasm, which may lead to the onset of asthma symptoms.

Potential Risks of Spirometry:

Potential risks include possible lightheadedness or wheezing.

Potential Risks of Mucociliary clearance scan:

The radiation risks for the MCC scan, including the Cobalt 57 transmission scan and the Americium 241 disks, which are used as fiducial markers is approximately 133 mRems. Adults in the New York City area receive about 300mRems per year in natural radiation exposure.

Potential Risks of Sputum Induction:

- Sputum induction may induce cough, chest tightness or bronchospasm **Protections Against Risk:**

Protections to Minimize Risk of Hypertonic Saline Inhalation:

A CEMALB physician is present in the building at all times during HS inhalation. All asthmatic subjects are pretreated with albuterol inhalation prior to hypertonic saline administration. Additional albuterol will be given after HS inhalation if FEV declines by $\geq 10\%$ from that day's baseline at the 30 minute spirometry measurement, if the participant develops symptoms of an asthma attack such as wheezing, or if the participant requests albuterol treatment.

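### Section 4.5 sets the Visit 5 FEV1 limit relative to screening at one tenth of baseline, which excludes no one and does not match the within-10% criterion in section 4.11

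*Combined protocol and SAP*

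**What the plan says.** Section 4.5 (Visit 5) gives two FEV1 conditions in one sentence. The first is relative to screening: "FEV1 must be at least 10% of baseline (established at screening visit"). The second is an absolute floor of 70% of predicted, which the next sentence repeats. The section then continues: "Participants will then inhale Tc99m-SC and immediately be scanned by gamma scintigraphy". Four puffs of albuterol, a 15-minute wait and 4 mL of nebulized 7% HS follow.

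Section 4.11 lists safety criteria to be met before HS. Two concern FEV1: at least 70% of predicted, and "within 10% of baseline value established at the screening visit". The list is binding: "Subjects not meeting these criteria will not proceed with HS inhalation".

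Section 4.3 (Visit 3, albuterol alone) has only the 70% floor. The clause relative to screening therefore appears in the visit instructions only where HS is to be given.

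**The concern.** Both sections compare Visit 5 FEV1 with the same screening value and both use the figure 10%, but they mean different things. Section 4.11 keeps the subject close to the screening value. Section 4.5, as worded, lets FEV1 fall to a tenth of it. No other part of the document supports a floor of 10% of baseline, and the likeliest explanation is a slip for 'within 10%'.

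The clause has a purpose. After HS, the FEV1 stopping rule (sections 4.11 and 5.3) is measured from that day's own baseline, so a subject who arrives well below screening is judged against the lower value. The comparison with screening before HS is the only numerical FEV1 check that would detect such a fall. Section 5.3 treats a 10% fall after HS as an adverse event leading to withdrawal, so a clause that allows far larger falls before HS cannot be what was meant.

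At stake is whether the Visit 5 instructions, which staff follow in order and which come before the radioaerosol, apply the limit the protocol intends.

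**Working it through.** **Inputs.** Let B be screening FEV1 in % of predicted.
- Section 4.5: Visit 5 FEV1 at least 0.10 × B, and at least 70.
- Section 4.11: FEV1 within 10% of B, taken here on the low side as at least 0.90 × B, and at least 70.
- Section 3.4: enrolment requires B of at least 70.

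**Effective floors.**
- Section 4.5: max(70, 0.10 × B). The relative clause exceeds 70 only if B > 70/0.10 = 700. No subject can meet that, so the 4.5 floor is always 70.
- Section 4.11: max(70, 0.90 × B). The relative clause exceeds 70 once B > 70/0.90 = 77.8.

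For B from 70 to 77.8 the two sections therefore give the same floor. Above 77.8, Visit 5 values from 70 up to (but not including) 0.90 × B pass 4.5 and fail 4.11.

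**Illustration.** The screening values below are chosen for illustration; the documents give no distribution of B. The largest fall that passes 4.5 is 100 × (1 − 70/B).

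| Screening FEV1 (% predicted) | 4.5 floor | 4.11 floor | Passes 4.5, fails 4.11 | Largest fall passing 4.5 |
|---|---|---|---|---|
| 75 | 70 | 70 (0.90 × 75 = 67.5) | none | 6.7% |
| 80 | 70 | 72 | 70 to below 72 (2 points) | 12.5% |
| 90 | 70 | 81 | 70 to below 81 (11 points) | 22.2% |
| 100 | 70 | 90 | 70 to below 90 (20 points) | 30.0% |

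**Direction of the 4.11 limit.** Section 4.11 does not say whether a rise above screening also counts. Read literally as two-sided, it would also bar HS above 1.10 × B, for example above 88 when B = 80. Section 4.5 has no upper limit, so on that reading the sections would also differ on the high side, at any B. The finding does not depend on this, but the wording of the fix does.

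**Order of steps.** Section 4.5 puts spirometry and its FEV1 conditions before the radioaerosol and lists no further spirometry before HS. The FEV1 that 4.11 tests is thus normally already known when 4.5 is applied.

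**The case against.** The strongest reply is that 4.11 governs. It is categorical, it is stricter, and a subject can satisfy both sections at once, so the protocol applied as a whole withholds HS from anyone outside the limit. That stands. It makes this a wrong threshold and a mismatch between sections, not a logical contradiction.

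Three stronger readings are tempting, and the documents support none of them.

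- *HS will be given to subjects far below their screening FEV1.* This needs staff to disregard the mandatory list in 4.11. Other safeguards also narrow the risk. The synopsis says that Not Well Controlled subjects "must be free of wheezing, and must be at their baseline prior to any hypertonic saline inhalation". Section 3.4 excludes abnormal lung auscultation, and 4.5 allows delay after an exacerbation. Under section 5.3, "HS treatment will be deferred if baseline total symptom score > 2". Albuterol pretreatment and direct physician supervision apply throughout. None of these is a numerical FEV1 limit, so they do not replace the missing clause, but they reduce its consequence.
- *Subjects will receive a wasted radioaerosol dose, and a further dose at a repeat visit.* Section 4.11 says only that its criteria apply before HS; nothing places that check after the radioaerosol, and the deciding FEV1 is available earlier. Nor does the protocol provide for repeating a scan in this situation. The line in section 3.1, "Subjects will simply be rescheduled if they have a change in health status", concerns changes in health. Section 9 gives a radiation figure ("which are used as fiducial markers is approximately 133 mRems") without making clear whether it is per scan or for all three. No radiation total can be built on this.
- *The primary analysis is affected.* Nothing in the documents shows that it would be.

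It can also be said that this is only a typing error. Probably so, but it is in a safety threshold in the instructions for the one visit at which nebulized 7% HS is given, and staff should not have to work out that the number must be disregarded.

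**Conclusion.** The point holds in a limited form. The screening-relative clause in 4.5 is wrong as written: it excludes no one beyond the 70% floor, and it does not match the mandatory criterion in 4.11. With 4.11 read on the low side, the sections differ only for subjects screened above 77.8% of predicted.

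The practical consequence is that the check preceding the radioaerosol does not apply the intended limit. Staff relying on 4.5 could start Visit 5 for a subject whom 4.11 excludes from HS. The documents give neither the distribution of screening FEV1 nor its variability between visits, so the number of the 28 subjects affected cannot be derived and may be zero. Severity is minor.

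**What to change.** Replace the clause in 4.5 with the limit in 4.11, for example: *FEV1 must be within 10% of the baseline value established at the screening visit and ≥70% of predicted*, and state that this is checked before Tc99m-SC is given.

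If only a fall is meant to bar HS, write *no more than 10% below* in both 4.5 and 4.11. Changing 4.5 alone to a one-sided limit would create a new mismatch: a subject 12% above screening would pass 4.5 and fail a literal reading of 4.11.

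The cost is a short wording amendment. No procedure is added, because 4.5 already places spirometry before the radioaerosol, and the analysis does not change.
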